1.0 BACKGROUND

Cardiac resynchronization therapy (CRT) is an established therapy for symptomatic heart failure patients despite optimal medical therapy with prolongation of QRS duration on surface electrocardiogram. Several pivotal studies have demonstrated a significant benefit in terms of mortality and morbidity in patients described above.¹⁻⁷ However, there are still 30 to 40% of studied patients being nonresponder to CRT, despite its proven benefit. The responder rate is particular poor in patients with non-LBBB pattern of conduction disturbance⁸⁻¹⁵ with one recent study showing non-LBBB patients has a responder rate of only 38%.¹⁵ The plausible reasons of lack of effect of CRT in these patients include relative less baseline electrical dyssynchrony, a homogenous type of conduction delay without a discrete line of block, lack of electrical ventricular uncoupling and inability to improve or even in some case worsening of electrical dyssynchrony with CRT.¹⁵⁻²¹ The electrical activation response to conventional CRT varies between individual patients may not be predicted by baseline conduction disturbance.^{10,17,19,22} The prevalence of non-LBBB type of conduction disturbance is reported to be as high as 44% in heart failure patients with increase in QRS duration.²³ Hence, a large proportion of heart failure patients with prolonged QRS duration will not benefit from CRT.

The quest to improve CRT responder rate has been subject of intense research interest. Apart from screening for subgroup of heart failure patients with better responder rate to conventional CRT, another possibility is to improve the efficacy of current CRT delivery system. There are two major approaches that have been studied to improve CRT delivery namely selecting the optimal site for LV pacing and alternate method of CRT delivery other than pacing at single epicardial LV site. Study have demonstrated that targeting the LV lead to the site of latest mechanical contraction as determined by strain echocardiogram improved the responder rate.²⁴ Other studies looks into local electrogram guided placement of LV lead to the latest electrically activated segment inside coronary sinus branch.²⁵ Regarding alternate way of CRT delivery, there are interests in using direct His-bundle pacing to overcome the longitudinal conduction delay in the His-Purkinje system. It has been shown that significant narrowing of QRS duration and favorable clinical outcome when compare to conventional CRT can be achieved with direct His-bundle pacing.²⁶ Intuitively, direct-His bundle pacing may provide benefit over pre-excitation of the left ventricle by conventional CRT in patients with right bundle branch block (RBBB) pattern of conduction disturbance. Other potential method to improve CRT outcome is the delivery of multipoint pacing (two LV sites together with one RV site and two RV sites together with one LV site) by recruiting more myocardium to contract simultaneously.²⁷⁻²⁹ Pacing the LV endocardium as compared to epicardium via a coronary access has been shown to improve acute hemodynamic response but however there is no long-term clinical result of endocardial LV pacing comparing to epicardial LV pacing.³⁰

The ability to deliver CRT using different configuration provides opportunity to tailor made resynchronization therapy to heterogenous group of patient in terms of activation delay. This is in contrary to the current concept of a single configuration of CRT deliver suit all patients with widening of QRS duration disregard of pattern of activation delay. Hence the aim of our study is to

investigate whether there is an optimal configuration of CRT delivery that varies between patients with different pattern of activation delay.

Previous study on noninvasive activation pattern has shown that responders showed higher degree of baseline dyssynchrony and greater improvement of dyssynchrony by CRT when compared to nonresponders.¹⁷⁻¹⁹ The optimal configuration of CRT delivery is defined by that result in the greatest improvement of electrical dyssynchrony. The acute change in electrical dyssynchrony indices will be compare between the optimal configuration and the conventional configuration, namely biventricular pacing with single LV lead in posterior or lateral branch of coronary sinus. A significant different between the two configurations would suggest that there indeed is an optimal configuration of CRT delivery and a tailor made strategy is feasible. To prove this concept of tailor made strategy, devices will be implanted to deliver CRT using the optimal configuration determined by noninvasive electrical activation mapping in non-LBBB patients. The medium term improvement of surrogate marker of LV systolic volume will be compared to that of a predefined level of 40%.

Our group has been using echocardiogram to study mechanical dyssynchrony in patients with heart failure and pacing induced LV dysfunction in predicting response to CRT.³¹⁻⁴⁷ However, in subsequent multi-center trial studying 12 different echocardiographic parameters of mechanical dyssynchrony in predicting CRT response, no single echocardiographic measure of dyssynchrony was shown to improve patient selection for CRT.⁴⁸ The results of the study further strengthen the concept that the response to conventional CRT therapy cannot be predicted by baseline dyssynchrony pattern. It is rather the degree of improvement from baseline that will predict response to CRT therapy. The degree of dyssynchrony improvement on the other hand is determined by the interaction of baseline electrical substrate and the activation change brings about by CRT. The electrical substrate is fixed but different configuration of CRT delivery, including different location of LV lead, can produce different changes in activation. In order to study the interaction of electrical substrate and change in activation brings about by CRT, a tool that allows global electrical mapping of both the LV and RV is considered to be important not only to elucidate important information like location of conduction block but also to study the interaction of the left and right ventricle.^{17-19,22}

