2.0 STUDY OBJECTIVES

The purpose is to prospectively study the feasibility to optimize configuration of CRT delivery for acute correction of electrical dyssynchrony using a noninvasive mapping of global electrical activation.

Study Hypothesis

Tailor-made configuration of CRT delivery is feasible and able to improve responder rate compare to single method of CRT delivery in candidates with known poor response to CRT.

Primary outcome measure

Responder rate of greater than 10% of LV end systolic volume reduction in patients undergoing tailor-made approach of CRT delivery at 6 months. The responder rate is to compare with pre-defined level of 40% for single method of CRT delivery namely biventricular pacing with LV lead in coronary sinus.

Secondary outcome measures

1. The acute electrical dyssynchrony indices of different methods of CRT delivery.
2. The hemodynamic responses of different methods of CRT delivery.
3. Procedure duration and implantation success rate of the optimal CRT delivery method as determined by the best improvement in electrical dyssynchrony indices.
4. Cine images (PA, LAO 30°, RAO 30°) and Chest X ray (PA view)
5. Peri-operative and 6 months follow-up complications rate:
 - a. Thromboembolic event
 - b. Dislodgement and migration of pacing leads
 - c. Phrenic nerve stimulation
 - d. Others
6. Echocardiogram parameters at baseline and 6 months: left ventricular systolic and diastolic volume, left ventricular ejection fraction, degree of mitral regurgitation, strain imaging.
7. NYHA class, 6 minute hall walk test and quality of life using Minnesota's questionnaire at baseline and 6 months.
8. Electrical parameters including threshold, sensitivity and lead impedance of pacing leads at implant and 6 months follow-up.

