6.0 PROTOCOL DESCRIPTION

Patient informed consent

The investigator is responsible for obtaining informed consent from each prospective study patient prior to the performance of any study related procedures. After a patient has been provided with the information of the study and given time to think on whether to participating into the study, the patient will be asked to sign and date a consent form. One copy of the signed patient consent form must be handed out to the patient and one must be filed by the investigator in the investigator files. After the patient and the investigator have signed and dated the consent form, the study data collection process may start.

Patients meeting all the inclusion criteria and not meeting any of the exclusion criteria are eligible for the study. Data will be collected at the following study visits:

Enrollment

Noninvasive electrical activation and acute hemodynamic study

Implant

[figure not shown]
Pre-discharge (PDH) (\leq 72 hours post implant)

Month 3 follow-up visit: 90 ± 14 days post implant

Month 6 follow-up visit: 180 ± 14 days post implant

Table 1. Data collection for each scheduled visit

	Enrollment	Implant *	PDH*	Month 3	Month 6
Patient Informed Consent	x				
Echocardiogram	x		x	x	x
Medical History	x				
Cardiovascular Medication	x	x	x	x	x
NYHA Class	x			x	x
6MHW	x			x	x
SF-36QoL	x			x	x
12-lead electrocardiogram	x	x		x	x
Cine images		x			
Device Interrogation		x	x	x	x
Adverse Event	x	x	x	x	x
Protocol Deviation	x	x	x	x	x

Figure 1. Study Flow Chart

Noninvasive mapping of electrical activation

Ventricular activation maps will be acquired simultaneously with hemodynamic measurements using noninvasive mapping system (ECVUE, Medtronic Inc, USA). A thoracic computed tomographic scan will be acquired with the electrodes attached to the patient. Local ventricular activation times will be defined as the onset of the QRS complex or the pacing spike to the maximal negative slope of each unipolar electrogram.

The following electrical dyssynchrony indices will be derived

- i) Total activation time (TAT) is defined as the time difference between the earliest and latest site of activation on the entire ventricular epicardium (LV and RV);
- ii) RVTAT is defined as the time difference between the earliest and latest site of activation on the RV ventricular epicardium;
- iii) LVTAT is defined as the time difference between the earliest and latest site of activation on the LV ventricular epicardium;

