- iv) Ventricular electrical uncoupling (VEU) is defined as mean LV activation time minus mean RV activation time (LVTAT-RVTAT)
- v) Intra-LV electrical dyssynchrony index (ED) is the standard deviation of activation times at 500 sites on the LV epicardium, including the epicardial aspect of the septum.

Placement of electrophysiology catheters for CRT delivery

Pacing leads will be placed in high right atrium, His-bundle region, right ventricular apex, high septal RV, coronary sinus posterior/lateral branch, coronary sinus anterior branch, lateral and septal region of endocardial LV in order to deliver CRT in 8 different configurations as stated below:

- 1) Conventional biventricular pacing with RV lead in right ventricular apex and LV lead in lateral or posterior branch of coronary sinus
- 2) Biventricular pacing with the LV lead in coronary sinus in closest possible proximity to the latest electrical activation region (18 region) if it is different to the site tested in (1)
- 3) Direct His-bundle pacing
 - i) His bundle pacing catheter distal tip as cathode and RV lead proximal pole as anode
 - ii) His bundle pacing catheter distal tip as cathode and proximal pole of LV lead placed in lateral or posterior branch of coronary sinus as anode.
 - iii) His bundle pacing catheter distal tip as cathode and His bundle pacing catheter proximal pole as anode.

In subjects in sinus rhythm

- i) together with RV bipolar pacing with RV lead in RV apex.

In subjects in AF

- i) together with RV bipolar and LV bipolar pacing

4) Multi-point pacing

- i) Triple site pacing with two RV leads in the RV apex and high RV septum and LV lead in posterior or lateral branch of coronary sinus.
- ii) Triple site pacing with RV lead in the RV apex and one LV lead in posterior or lateral branch of coronary sinus and the other LV lead in anterior branch of coronary sinus.
- iii) Triple site pacing with RV lead in RV apex and one quadripolar LV lead in posterior or lateral branch of coronary sinus and pacing at 2 sites simultaneously from the quadripolar lead.

During delivery of CRT the output will be set at twice the capture threshold and pacing impulse will be delivered in VDD mode with an AV delay of 80msec and VV delay at 0msec for all leads in the ventricles.

Acute hemodynamics studies

Invasive LV hemodynamic measurements of LV dP/dt will be recorded using a micromanometer (Radi Medical Systems, St Jude Medical, USA) placed in the LV cavity.

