All measurements will be made with an average of 10 second recordings with no occurrence of premature atrial or ventricular beats during the recording and 1 minute interval between changes in pacing settings.

During sinus rhythm and the 7 configurations of CRT pacing as stated above both noninvasive electrical activation map and acute hemodynamic measurement will be recorded for analysis.

Implantation of CRT device**1) Conventional pacing configuration**

The CRT system will be implanted with standard technique for conventional pacing configuration. Only market released CRT devices and leads will be implanted.

2) Epicardial LV pacing in the latest activation site

LV lead will be placed in the LV latest activation site or the site in closest proximity to the latest activation site and if necessary quadripolar or active fixation LV lead will be used to achieve stability.

3) Direct His-bundle pacing

i) In subjects in sinus rhythm

For direct-His bundle pacing, standard techniques will be used to place an LV lead preferably in the posterolateral branch of the coronary sinus system, RV and right atrial lead. His pacing lead (SelectSecure, model 3830, Medtronic Inc, USA) supported using a dedicated delivery sheath (model C315, Medtronic Inc, USA) or a deflectable lead delivery sheath (model C304, Medtronic Inc, USA) to the site showing His bundle signal on the mapping catheter. Multiple position to optimize QRS narrowing and threshold could be tested. The His pacing lead and the LV lead will be connected via a Y-adapter (model 5866-38M, Medtronic Inc, USA). The HBP will be connected to the cathode and the LV tip to the anode of the Y-connector.

ii) In subjects in AF

The same as for subjects in sinus rhythm except the His pacing lead will be connected to the atrial port of the CRT device and LV lead into the LV port of the CRT device without the use of a Y adapter.

4) Multiple point pacing

For multiple point pacing, the septal RV and the bipolar LV leads will be connected to the LV port using a parallel Y-adapter (model 2872, Medtronic Inc, USA) for the 2 RV leads group. Whilst the anterior bipolar and posterior/lateral LV lead will be connected using a parallel Y-adapter (model 2872, Medtronic Inc, USA) for the 2 LV leads group. If simultaneous pacing from 2 sites or the quadripolar LV lead pacing is the optimal configuration, a quadripolar lead will be connected to the LV port.

CRT programming

Para meter	Mandatory Device Setting
Mode	DDD or DDDR

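### The rule that picks the implanted configuration names no deciding index among five, so the tailored strategy is not reproducibly defined; separately, the acute optimal-versus-conventional comparison is biased by selection

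*Combined protocol and SAP*

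**What the plan says.** Section 1.0 (Background) gives the selection rule: "The optimal configuration of CRT delivery is defined by that result in the greatest improvement of electrical dyssynchrony". It adds that devices will be implanted in the configuration found by mapping. It also says that optimal and conventional configurations will be compared on the acute change in the dyssynchrony indices, and that a significant difference would suggest an optimal configuration exists and tailoring is feasible.

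Section 2.0 restates the rule among the secondary outcomes, now in the plural: the "optimal CRT delivery method as determined by the best improvement in electrical dyssynchrony indices".

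Section 6.0 (Noninvasive mapping) says "The following electrical dyssynchrony indices will be derived" and lists five:

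- TAT: activation span of both ventricles.
- RVTAT: span of the RV alone.
- LVTAT: span of the LV alone.
- VEU: "Ventricular electrical uncoupling (VEU) is defined as mean LV activation time minus mean RV activation time (LVTAT-RVTAT").
- ED: "Intra-LV electrical dyssynchrony index (ED) is the standard deviation of activation times at 500 sites on the LV epicardium".

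On the number of candidates, section 6.0 says catheters are placed "in order to deliver CRT in 8 different configurations as stated below", and later that recordings are made "During sinus rhythm and the 7 configurations of CRT pacing as stated above". Conventional biventricular pacing is the first on the list. Section 5.0 offers a t test or a nonparametric equivalent for additional analyses, with no provision for selection or for several indices.

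**The concern.** The rule that defines the intervention has to return one answer per patient. Here it can return several. The five indices describe different parts of the heart and different features of activation, so one configuration can be best on one index and not on another. For a signed quantity such as VEU, greatest improvement has no meaning until a direction or target is stated. Two competent teams with the same map could follow the protocol faithfully and implant different systems. A 6-month responder rate above 40% would then belong to a strategy that another centre could not repeat.

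The acute comparison raises a different problem. The winner of a contest is compared with one of the other entrants on the scores that decided the contest. Measurement error alone produces a winner, and the comparison credits that error as benefit. Section 1.0 intends to read a significant difference as showing that an optimal configuration exists, and this design cannot support that reading.

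**Working it through.** **Is there a deciding index?** The rule and the definitions, side by side:

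| Place | What it supplies | What it leaves open |
|---|---|---|
| 1.0 | Greatest improvement of dyssynchrony | Which measure |
| 2.0 | Best improvement in indices, plural | Which one, or how combined |
| 5.0 | Generic tests | Any selection rule |
| 6.0 | Five definitions | Ranking, composite, direction, tie-break |

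The VEU entry has a further ambiguity. It equates a difference of mean activation times with LVTAT minus RVTAT, but section 6.0 defines those two as earliest-to-latest spans, not means.

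**How often could the choice of index matter?** The documents give no SDs or correlations, so this is an illustration. Assumptions: 8 configurations, five equally correlated indices with correlation r, standard normal improvements, no true difference between configurations, 100,000 simulated patients.

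| r | Two indices pick the same configuration | All five do |
|---|---|---|
| 0.3 | 23% | 1% |
| 0.5 | 33% | 5% |
| 0.7 | 46% | 16% |
| 0.9 | 67% | 41% |

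With 7 configurations, pairwise agreement runs from 25% to 68%.

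**What gain does selection alone produce?** Let Y₁ be the measured improvement under conventional pacing and Y₁,…,Yₖ those of all k candidates, with equal independent errors of SD 1 and no true difference.

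- Gain = max(Y₁,…,Yₖ) − Y₁, which is at least 0 because Y₁ is in the set.
- Expected gain = E[max of k standard normals] − 0 = 1.35 SD for k = 7 and 1.42 SD for k = 8.
- Chance that conventional is not the winner = 1 − 1/k = 0.86 for k = 7 and 0.875 for k = 8.
- A paired two-sided 5% t test on this gain (k = 8, one fixed index) rejects in about 60% of null trials at n = 5, 99% at n = 10 and essentially all at n = 20 or more.

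If the index with the largest gain is chosen per patient after the maps are seen, the expected gain at k = 8 becomes 2.5, 2.4, 2.2 and 1.9 SD for r = 0.3, 0.5, 0.7 and 0.9. At k = 7 the range is 2.5 to 1.8 SD.

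**Which source is larger?** The fixed-index part is 1.42/2.5 = 57% to 1.42/1.9 = 75% of the total. More than half of the null gain would therefore remain after one index had been designated.

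**What if configurations truly differ?** Let the true between-configuration SD be τ times the measurement SD. The expected error carried by the winner is 1.42/√(1+τ²), and its share of the observed gain is 1/(1+τ²).

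- τ = 2: 1.42/√5 = 0.63 SD, a share of 20%.
- τ = 3: 1.42/√10 = 0.45 SD, a share of 10%.

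**On data not used for selection,** with errors independent of the selecting recording and no true difference, the expected gain is 0.

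**The case against.** Several points on the other side are sound.

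- **Timing.** Mapping precedes implant, and implant precedes the 6-month echocardiogram. A reader might infer that the index could be chosen with the outcome in view and the responder rate inflated. The visit order in section 6.0 rules that out. What is missing is a choice fixed before the map is seen.
- **Who chooses.** A reader might also infer that the operator sees all five indices and may use any of them patient by patient. The documents do not say who selects or what that person sees. Their silence is an omission and not a permission.
- **Devices versus configurations.** The simulation counts 8 separate choices. Section 6.0 tests three His-bundle electrode variants but describes one His implant arrangement for sinus rhythm, which is the eligible rhythm in section 3.0. Collapsing those leaves 8 − 2 = 6 arrangements, and pairwise agreement rises to 31%, 40%, 52% and 70%. Disagreement between indices therefore does not always mean a different implant.
- **Realism.** Equal positive correlation does not fit these indices. VEU is written as a difference of two of the others and cannot be equally and positively correlated with both. True differences between configurations would also shrink the bias, as the working shows.
- **Status of the comparison.** It is described in the Background. Section 2.0 lists only the indices by method as a secondary outcome.
- **Figure 1.** The flow chart is not shown in the text available, so a selection rule there cannot be excluded.

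These limit the sizes and rule out the stronger readings. They do not supply a deciding index in the visible text, and they do not make the same-index comparison unbiased.

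**Conclusion.** The point holds, in two separate parts.

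First, the selection rule is incomplete in a way that matters, because it decides what is implanted. The tailored strategy is not reproducibly defined. This rests on the text alone, subject to Figure 1, and needs no simulation. It does not bias the 6-month responder rate.

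Second, the acute comparison is biased towards a gain on the selecting index whatever the correlations. Under no true difference and equal independent errors, the size is about 1.4 SD on one fixed index and about 1.9 to 2.5 SD with free choice per patient. These are illustrations and not estimates for this trial. If true differences are two to three times the measurement error, the fixed-index bias falls to about 0.6 to 0.45 SD.

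A reader might conclude that naming one index repairs the acute comparison. It does not. It removes the ambiguity and the extra inflation from free choice, but the larger part comes from taking the best of 7 or 8 configurations and scoring it on the data that selected it.

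**What to change.** **Selection rule (sections 2.0 and 6.0).** Before the first patient, designate one index as the sole selection index, with its direction of improvement and a tie-break. Which index is the investigators' choice. If it is VEU, also state which of the two expressions in its definition applies. Report the other four descriptively. Reconcile the 7 and 8 configurations so that the candidate set is fixed.

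**Acute comparison (sections 1.0 and 5.0).** Do not read a significant same-recording difference on the selection index as evidence that an optimal configuration exists. Base that inference on data not used for selection. Two sources are at hand:

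- LV dP/dt, which section 6.0 already records for the tested configurations. It answers a haemodynamic question, not an electrical one.
- A held-out part of the recordings. Errors common to both parts, such as those from electrode position or imaging, would remain.

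Both come from the same session, so independence of errors should be stated as an assumption. Show the same-index gain as descriptive and label it selection-biased.

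**Cost.** A few sentences and no extra patients. The sponsor gives up flexibility in the choice of index and should expect a less favourable acute result.

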5.0 STATISTICAL CONSIDERATION

Hypothesis

The null and alternative hypotheses are as follows:

H0: The responder rate of tailor-made approach \leq 40%

HA: The responder rate of tailor-made approach $>$ 40%

Sample size was calculated employing binomial methods with the following assumptions were used:

Expected responder rate for tailor-made approach =60%

Historical control responder rate =40%

Test significance level (a) = 0.05 (1-sided)

Power= 80%

Based on the above assumptions, the sample size was calculated as 77. Accounting for the attrition of 20%, the total required sample size is 93 patients with device implanted.

Statistical method for additional analysis

All continuous data will be summarized with the number of non-missing data, mean \pm standard deviation, median and range (minimum – maximum). T test will be used for the comparison between the groups. In case the assumption for t test is violated, then the equivalent nonparametric test, such as Wilcoxon rank sum test, Kolmogorov-smirnov test, will be used instead. The normality assumption will be tested by the normality test with the aid of QQ plot.

All categorical data will be tabulated with number of occurrence and percentage. Chi-square test will be used for the comparison between the groups. In case the expected counts in each cell is less than 5, then Fisher's exact test will be used instead.

Procedures for reporting any deviation(s) from the original statistical plan

Any deviations from the statistical analysis plan will be documented.

The treatment of missing, unused or spurious data, including drop-outs and withdrawals.

No imputation techniques will be used.

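### The optimal configuration is the best of a set that includes conventional pacing, so a significant acute gain over conventional pacing does not show that an optimum exists

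*Combined protocol and SAP*

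**What the plan says.** The aim at the start of section 1.0 is to "investigate whether there is an optimal configuration of CRT delivery that varies between patients with different pattern of activation delay". The same section gives the selection rule: "The optimal configuration of CRT delivery is defined by that result in the greatest improvement of electrical dyssynchrony". It then plans the contrast: "The acute change in electrical dyssynchrony indices will be compare between the optimal configuration and the conventional configuration". A significant result is read as follows: "A significant different between the two configurations would suggest that there indeed is an optimal configuration of CRT delivery". The same sentence extends that reading to the feasibility of tailoring.

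Section 2.0, secondary outcome 3, repeats the selection rule: the implanted method is the optimal one "as determined by the best improvement in electrical dyssynchrony indices". Secondary outcome 2 is separate: "The hemodynamic responses of different methods of CRT delivery".

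In section 6.0, conventional biventricular pacing is item 1 in the list of configurations to be tested and option 1 for implantation. The mapping subsection says "The following electrical dyssynchrony indices will be derived" and lists five (TAT, RVTAT, LVTAT, VEU, ED), without naming the one that decides. The catheter subsection counts 8 configurations and the haemodynamic subsection 7. Configuration 2 is tested only if its site differs from that of configuration 1.

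For continuous data, section 5.0 offers "T test will be used for the comparison between the groups", with rank-based fallbacks. No repeat map, hold-out or adjustment for selection is described.

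**The concern.** The same measurements choose the winner and then test it against one of the candidates. Measurement error alone makes the selected configuration look better than conventional pacing, because selection favours whichever configuration drew a lucky error. The contrast on the selecting index cannot come out unfavourable, so its significance is no evidence for the claim attached to it.

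There is a second gap. Even with error-free maps, a significant difference could arise because one configuration is better than conventional pacing for every patient. That would not show an optimum that differs between patients, which is the stated aim and the reason to tailor.

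At stake are the acute electrical result and the conclusion about tailoring that section 1.0 draws from it. The reported electrical gain would be overstated. Implantation success and the 6-month responder rate still bear on feasibility.

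**Working it through.** **Inputs.** The selection rule and contrast are from section 1.0. The number of configurations k is 8 or 7 (section 6.0); 5 and 6 are added in case some cannot be tested. N=77, or 93 with attrition, is from section 5.0 (77 × 1.2 = 92.4, rounded up). Those sizes were set for the responder rate; the plan gives no figure for the acute contrast. Assumptions: independent normal errors with SD σ, which the documents do not give, and a two-sided 0.05 level, since section 5.0 states a level (one-sided 0.05) only for the primary test. The main simulations used 4000 trials per setting.

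**Step 1: direction.** Let x_ij be the improvement in patient i under configuration j, with j=1 conventional. The patient's baseline is common to all configurations and cancels. The contrast is D_i = max_j(x_ij) − x_i1 ≥ 0, and it is zero only when conventional pacing is selected or ties. No distributional assumption is needed.

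**Step 2: size when all configurations are truly identical.** Mean D = σ × E_k, where E_k is the expected maximum of k standard normal values.

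| k | mean D / σ | conventional selected (1/k) |
|---|---|---|
| 5 | 1.16 | 20% |
| 6 | 1.27 | 16.7% |
| 7 | 1.35 | 14.3% |
| 8 | 1.42 | 12.5% |

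Assumed σ of 2, 5 and 10 ms gives 2.7–2.8, 6.8–7.1 and 13.5–14.2 ms for k = 7–8.

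**Step 3: paired test on the selecting index.** With identical configurations, rejection was 100% at N=77 and N=93 for every k in the table, and no within-patient difference was negative. At N=77 the average t statistic was about 11.3 (k=7) and 11.9 (k=8). With conventional pacing truly best by 1σ, the apparent gain was still 0.62–0.67σ; by 2σ, 0.20–0.22σ. Rejection was 100% in both cases.

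**Step 4: the between-group t test worded in section 5.0.** Rejection with identical configurations, by ratio of error SD to between-patient SD (k=7 to k=8):

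| ratio | N=77 | N=93 |
|---|---|---|
| 0.10–0.15 | about 0% | about 0% |
| 0.20 | 6%–15% | 24%–40% |
| 0.25 | 65%–79% | 89%–96% |
| 0.30 | 96%–99% | about 100% |

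The low rates at small ratios arise because this test ignores that both values come from the same patient; it does not remove the bias in the mean.

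**Step 5: when real differences exist.** If true effects vary within patient with SD τσ, the overstatement is σE_k/√(1+τ²), which is a share 1/(1+τ²) of the apparent gain. For τ = 0.5, 1 and 2 and k = 7–8 this is 1.21–1.27σ (80%), 0.96–1.01σ (50%) and 0.61–0.64σ (20%).

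**Step 6: testing a measure other than the selecting one.** With identical configurations, k=8 and N=77, a paired test on a measure whose errors correlate with the selecting index at 0, 0.1, 0.2, 0.3 and 0.5 rejects in about 5%, 16%, 45%, 81% and 100% of trials.

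**The case against.** The strongest reply concerns weight. The sentence is in the background, says only that a difference would suggest an optimum, and is followed by text that leaves proof of the concept to the 6-month responder rate against 40%. Section 5.0 gives the acute contrast no hypothesis and no alpha. This stands and limits the severity. But it is the only place where the plan says how this comparison will be interpreted, and that interpretation is wrong as written.

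Second, the 100% figure belongs to a paired test that the plan does not specify. That is true, and for the worded test the rate depends on an unknown SD ratio. A between-group test does not suit two configurations measured in one patient, so it offers no defence.

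Third, selection might use a combination of the five indices. Then only the combined score is favourable by construction. With the mean of five equal-variance indices, k=8, identical configurations and error correlation between indices of 0 to 0.8 (all assumed), 26% down to 6% of patients would show an unfavourable difference on a given index. The mean gain is still biased upward, by 1.42 × √((1+4ρ)/5) = 0.64 to 1.31 error SDs.

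Fourth, identical configurations are the extreme case, and averaging 10-second recordings should reduce error. Step 5 allows for this; at τ=2 the overstatement is 20% of the gain.

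Fifth, one configuration better for everyone would satisfy the literal statement that an optimum exists. It would, but it would not support tailoring or variation between patients.

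**Conclusion.** The concern holds. On the selecting index the contrast cannot be unfavourable, and its significance does not support the conclusion drawn in section 1.0. The direction is exact for a single selecting index or a fixed combined score. The size rests on an error SD that the documents do not give: 1.35–1.42 error SDs if the configurations are identical, less if they truly differ. The 100% rejection rate applies to a paired test on that index at two-sided 0.05. Other indices are biased only as far as their errors correlate with the selecting one, and since none is named, the plan cannot show that any is free of bias. The primary comparison with 40% does not use this contrast and is unaffected. This should be corrected, but it does not threaten the primary analysis.

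**What to change.** 1. In section 1.0, remove the statement that a significant difference suggests an optimal configuration. Report optimal minus conventional on the dyssynchrony indices as descriptive, and state that selection biases it upward.
2. Before the first mapping study, name the single index or fixed combination that selects the optimal configuration.
3. Add a supportive paired analysis of LV dP/dt, optimal minus conventional. It is already recorded in each configuration and does not drive selection. Count patients whose optimum is conventional as zeros. Use a paired t test or, if needed, a signed-rank test with Pratt's handling of zeros. State that it measures haemodynamic rather than electrical benefit, that correlated errors leave bias (maps and pressures are recorded at the same time), and that it does not show that the optimum varies between patients.
4. Optionally, report the share of patients with a non-conventional optimum beside a chance value of 1 − 1/k from each patient's own number of tested configurations (80%, 83.3%, 85.7% and 87.5% for k = 5 to 8). Label it as assuming exchangeable, independent errors.
5. Reconcile the two counts of configurations in section 6.0, given the condition on configuration 2.

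Items 1 and 2 follow directly from the flaw and need only text. Item 3 uses planned data and adds no procedure or patient. Its cost is uncertainty. Mapping precedes implantation, so about 93 patients should contribute. At that N its power is about 31%–34%, 69%–74% or 94%–96% if true effects on the two measures vary with SD 1 error SD and correlate 0.3, 0.5 or 0.7, so a non-significant result would not show absence of benefit. It would reject falsely in about 17%–19% of trials at an error correlation of 0.1, and in about 72%–80% when one configuration is better for everyone by 1 error SD and no tailoring is needed.

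An independent repeat map of the two configurations would keep the electrical question, with 4%–5% rejection when configurations are identical. It would lengthen an invasive study, and error shared by both maps would leave bias (14%–16%, 43%–47% and 79%–82% rejection at 10%, 20% and 30% shared variance). Items 1 and 2 do not depend on it.
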